9.3.3. Secondary Endpoints Analysis

The ITT analysis set will be used for the main analysis of key secondary and exploratory endpoints. Subjects will be included in analyses as randomised. All collected data post-intervention will be used to assess the endpoints. The key secondary endpoints are:

- Change from baseline in clinician-reported anxiety symptom severity as assessed by Hamilton anxiety rating scale (HAM-A) at Week 9
- Change from baseline in HRQoL assessed by K-BILD psychological domain score at Week 9
- Change from baseline in HRQoL assessed by K-BILD total score at Week 9

The key secondary endpoints will be tested in a pre-specified hierarchical order following the test of the primary endpoint. Other exploratory endpoints will be tested independently without adjustment for multiple tests.

The key secondary endpoints, change from baseline in HAM-A, K-BILD psychological domain and total scores at Week 9, will be compared between treatment groups using an ANCOVA model with treatment and strata (baseline anxiety severity) as factors and the baseline score as covariate.

Withdrawals from the clinical investigation prior to Week 9 not possible to follow-up will be imputed using multiple imputation taking subjects baseline characteristics, treatment, and post-treatment scores into account.

Other continuous endpoints assessed at baseline and post-intervention will be compared using similar ANCOVA models as for the primary (with interaction; GAD-7 based endpoints) or key secondary endpoints (without interaction) with treatment effect expressed as difference in mean scores. PGIC scores will be compared using a similar ANOVA model omitting the covariate. Endpoints assessing proportion of subjects (binary outcome) will be compared using logistic regression models adjusting for treatment and strata (baseline anxiety severity) as factors. Categorical endpoints will be summarized by category and compared using the chi2-test.

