9.3. Statistical Analyses

9.3.1. General Considerations

All tests will be 2-sided at a 5% significance level.

Baseline will be defined as the last non-missing assessment obtained prior to randomization.

Stratification will be done based on baseline disease severity defined as the total score on the GAD-7 questionnaire (GAD-7 score 5-9, 10-14 or ≥15 points) at baseline (Visit 1).

The actual stratification will be used as factors in the statistical analysis, subjects included in wrong stratum at randomization will be moved to their correct strata belonging in the analyses.

Continuous variables will be summarized using (arithmetic) means, standard deviation (SD), median, minimum, and maximum value, categorical variables will be summarized using numbers and percentages.

The ITT analysis set is used for the main analysis of all endpoints related to the efficacy objectives. Sensitivity analyses related to efficacy objectives will be described in the SAP. The safety analysis set is used to analyze the endpoints and assessments related to safety.

All data regarding subject characteristics, efficacy and safety will be listed.

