9.3.2. Primary Endpoint/Estimand Analysis

The primary endpoint, change from baseline in patient-reported anxiety symptom severity assessed by GAD-7 at Week 9, will be compared between treatment groups using an ANCOVA model with treatment and strata (baseline anxiety severity) as factors, the baseline GAD-7 score as covariate and the baseline by strata interaction.

The adjusted mean difference between groups will be given together with 95% confidence intervals and associated 2-sided p-value.

Withdrawals prior to Week 9 not possible to follow-up will be imputed using multiple imputation taking subjects baseline characteristics, treatment, and post-treatment GAD-7 scores into account.

The ITT analysis set will be used for the main analysis of the primary endpoint. Sensitivity analyses will be performed with alternative methods for imputation (for instance using the average of the opposite treatment group as base) and a tipping point analysis will also be performed investigating the impact on the treatment effect by successive shifts introduced in the imputation for the active group. Sensitivity analysis will be described in the SAP. In all analyses subjects will be included as randomised. All collected data post-intervention will be used to assess the endpoint.

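### Logistic models for binary endpoints adjust for the three GAD-7 strata only; adding the continuous baseline score, where one exists, would be a small gain at almost no cost

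*Combined protocol and SAP*

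**What the plan says.** Section 9.3.3 states that binary endpoints "will be compared using logistic regression models adjusting for treatment and strata (baseline anxiety severity) as factors". Sections 9.3.1 and 9.3.5 define the severity factor as three baseline GAD-7 bands: 5 to 9, 10 to 14, and 15 or more.

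The continuous endpoints get more:

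- The primary ANCOVA (Section 9.3.2) has treatment, strata, "the baseline GAD-7 score as covariate and the baseline by strata interaction".
- The key secondary endpoints (Section 9.3.3) use an "ANCOVA model with treatment and strata (baseline anxiety severity) as factors and the baseline score as covariate".
- Other continuous endpoints measured at baseline and afterwards follow one of these two forms.

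The one stated exception is PGIC: "PGIC scores will be compared using a similar ANOVA model omitting the covariate".

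On the population, Section 9.3.3 says: "The ITT analysis set will be used for the main analysis of key secondary and exploratory endpoints". The primary and all three key secondary endpoints are continuous. Any binary endpoint therefore lies outside the fixed testing sequence and is tested without multiplicity adjustment. The legible text names no binary endpoint and no responder threshold; these may have been blacked out, and I do not treat their absence as a fault.

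**The concern.** A three-level band is a coarse stand-in for the score behind it. Take a threshold of GAD-7 below 5. A subject who enters at 5 must fall by 1 point to reach it, and one who enters at 9 must fall by 5. Both are in the mild stratum, so the logistic model treats them as having the same prognosis.

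The gap is wider for a responder definition on a different scale, such as HAM-A or K-BILD. There the model adjusts for a GAD-7 category and not at all for the scale's own starting value, although the ANCOVA on the same scale does.

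What is at stake is some power for results that readers often use to judge clinical relevance. Validity is not at stake.

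**Working it through.** The plan gives no responder rate, SD, correlation, stratum mix or power for a binary endpoint, so there is no figure to reproduce. From the documents: two-sided 5% tests, 1:1 allocation, at most 250 subjects, and the three strata. Everything else below is assumed.

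**1. How much of baseline GAD-7 do the strata already capture?** Assume scores uniform within each band: 5–9 (mean 7, variance 2), 10–14 (mean 12, variance 2), 15–21 (mean 18, variance 4). With a 60/30/10% mix:

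- Mean = 0.6×7 + 0.3×12 + 0.1×18 = 9.6.
- Between-strata variance = 0.6×2.6² + 0.3×2.4² + 0.1×8.4² = 12.84.
- Within-strata variance = 0.6×2 + 0.3×2 + 0.1×4 = 2.2.
- Share explained = 12.84 / (12.84 + 2.2) = 85%.

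The same sum gives 81% for a 70/25/5% mix and 88% for 45/35/20%. Little is left for the continuous score to add when the endpoint is based on GAD-7.

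For another scale correlated 0.3 or 0.6 (in absolute value) with GAD-7, the strata explain only 0.3²×0.854 = 8% or 0.6²×0.854 = 31% of that scale's baseline variance. More can be recovered there.

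**2. Power for GAD-7 responders.** 1,000 simulated trials per scenario, effect 1.5 points, SD parameter 4 (residual SD 4√(1−ρ²)), Wald test. Selected results at N = 250:

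| Mix (%) | Correlation ρ | Responder definition | Strata only | Strata + score | Change (points) |
|---|---|---|---|---|---|
| 60/30/10 | 0.6 | score below 5 | 65.7% | 67.4% | +1.7 |
| 60/30/10 | 0.6 | fall of at least 4 | 79.9% | 80.4% | +0.5 |
| 60/30/10 | 0.6 | fall of at least 50% | 74.6% | 74.9% | +0.3 |
| 70/25/5 | 0.6 | score below 5 | 69.6% | 73.1% | +3.5 |
| 70/25/5 | 0.6 | fall of at least 50% | 75.0% | 74.4% | −0.6 |
| 60/30/10 | 0.4 | score below 5 | 61.4% | 61.2% | −0.2 |
| 60/30/10 | 0.8 | score below 5 | 77.3% | 82.4% | +5.1 |

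Over all scenarios at ρ = 0.6, including N = 120, the change runs from −0.6 to +3.5 points and is mostly under 2. The simulation standard error of one power value is about √(0.7×0.3/1000) = 1.4 points, so the small negative values are noise.

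A second simulation used 125 per arm, ρ = 0.46, an effect of 1.5 points and 1,500 trials. It gave 69.4% to 70.7% (+1.3) for a score below 5 and 77.2% to 78.7% (+1.5) for a fall of at least 4.

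**3. Power for responders on another scale.** 2,000 trials per scenario, effect 0.3 SD, response defined as an improvement of at least 0.5 SD, 60/30/10% mix, ρ from 0.5 to 0.8, correlation with GAD-7 of −0.3 and −0.6.

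- Largest gain (N = 250, ρ = 0.5, correlation −0.3): 44.85% to 50.0%, +5.2.
- Smallest gain (N = 120, ρ = 0.8, correlation −0.6): 48.7% to 50.25%, +1.5 (1.55 before rounding).
- The second simulation gave 70.6% to 73.5%, +2.9.

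**4. A stratum with no responders.** The chance that a stratum of n subjects with response probability p has no or only responders is (1−p)ⁿ + pⁿ. For n = 25 (10% of 250) it is 27.7% at p = 5%, 7.2% at 10% and 0.4% at 20%. In one worked data set with no responders in the severe stratum:

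| Model | Treatment log-odds ratio (SE) | Severe-stratum coefficient |
|---|---|---|
| Treatment + strata | 0.380 (0.272) | diverges (about −33, SE about 3,400) |
| Same, severe stratum removed | 0.380 (0.272) | not in model |
| Treatment + strata + score | 0.369 (0.273) | still diverges |
| Treatment + score, no strata | 0.391 (0.269) | not in model |

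**The case against.** The case for leaving the model alone is fair. Adjusting for the stratification factor is a valid analysis and keeps the type I error. The endpoints are exploratory and cannot be seen. Some may have no baseline: PGIC is one such measure, and its ANOVA drops the covariate for that reason. The gain for GAD-7 responders is often within simulation error. All of this stands. It limits the point to endpoints derived from a scale measured at baseline and keeps it minor. It does not explain why such an endpoint should be adjusted less fully than the ANCOVA on the same scale.

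The opening of Section 9 calls the section a summary and defers technical detail to the SAP, as Section 9.3.5 does again. That answers silence on handling rules. It does not answer the covariate list, which Section 9.3.3 does state.

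A reader might infer two stronger things:

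- **That leaving out the score can make the severity factor inestimable.** Step 4 does not support this. The divergence comes from a stratum in which nobody, or everybody, responds. Adding the score does not cure it. The affected coefficient is a nuisance term, and the treatment estimate was the same with and without that stratum.
- **That binary endpoints are planned as complete-case analyses.** No text says so. The multiple-imputation sentence in Section 9.3.3 follows the key secondary model but is not expressly confined to it, and the ITT set is assigned to exploratory endpoints too. The most that can be said is that the derivation of responder status for withdrawals is not spelled out.

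**Conclusion.** The point holds as a minor improvement. The logistic models omit a baseline score that the corresponding ANCOVAs use. For a responder endpoint on a scale measured at baseline, adding it should gain about 0 to 3.5 power points for GAD-7 at a correlation of 0.6 (up to about 5 at 0.8), and about 1.5 to 5 points on another scale.

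These figures rest on assumed stratum mixes, SD, effect sizes, correlations and responder definitions, none of which the legible text gives. They also rest on the assumption that such endpoints exist. Type I error, the primary analysis and the key secondary analyses are not affected.

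**What to change.** In Section 9.3.3 and the SAP, specify the logistic model as treatment, stratum, and the continuous baseline score of the scale from which the endpoint is derived. Keep strata only where no baseline exists.

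The one small downside is interpretive: the odds ratio becomes conditional on one more covariate. Report beside it a risk difference obtained by averaging model predictions over the trial population.

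Two confirmations belong in the SAP: that responder status is derived from the multiply imputed scores used for the continuous analysis, and what is done if a stratum has no events (for example a Firth-penalised fit or pooled strata).

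The cost is a few lines of SAP text and code before analysis. Data collection and trial conduct do not change.

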Part 2 part is a 9-week, randomised, assessor-blind, controlled, parallel-group clinical investigation with a 3-week follow-up period evaluating the impact of dCBT-PF on psychological symptom burden in adults with PF. Recruitment for Part 2 will continue until end July 2023, or when a maximum of 250 subjects with PF have been enrolled, whatever comes first. Subjects will be 1:1 to dCBT-PF or an open-label waitlist control group. Subjects in the

control group will receive access to dCBT-PF treatment after the follow-up visit at Week 12 (see Section 6.5).

Randomization will be stratified by anxiety severity based on the GAD-7 score at baseline:

Mild: 5-9 pointsModerate: 10-14 pointsSevere: >15 points

[figure not shown]
Approximately 400 subjects with PF are expected to be screened to achieve 250 enrolled and randomly assigned subjects.

Eligibility will be determined at pre-screening (V0) and baseline (V1), and eligible subjects will be randomised to either dCBT-PF or a waitlist control group. GAD-7 and K-BILD questionnaires will be completed at baseline, every 3rd week during the treatment period and at the end of the 3-week follow-up period.

All assessments will be conducted remotely via telehealth or phone calls i.e., no in-person visits. Individual subject participation in the clinical investigation from time of randomisation is expected to be approximately 12 weeks.

The primary endpoint is the change from baseline in anxiety symptom severity assessed by GAD-7 at Week 9. The key secondary endpoints are change from baseline in HAM-A, K-BILD psychological domain score and K-BILD total score at Week 9. Type 1 errors will be controlled using a fixed sequential testing hierarchy.

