The planned dCBT-PF treatment duration is 9 weeks with an intended daily use of 10 minutes. Traditional CBT conducted via sessions with a psychologist, or a psychotherapist can vary considerably in length and duration, with sessions lasting between 30 to 60 minutes and treatment containing 5 to 20 sessions (NHS, 2019). The dCBT-PF consist of 7 interventional CBT modules (Therapy modules) and 3 non-interventional modules (PF Essentials). A target treatment duration of 9 weeks in the pivotal part of the clinical investigation is considered justifiable based on both traditional and digital CBT experience.

To minimize bias, the clinical investigation will have a randomised, assessor-blind, controlled design. Subjects will be randomised 1:1 to dCBT-PF or an open-label waitlist control group and the randomization will be stratified by self-reported anxiety severity based on GAD-7 score to ensure an equal distribution in both groups (active and control).

Implementation of a placebo-app (sham) would not provide sufficient blinding and was considered to create substantial bias in the design of the clinical investigation. A clinician-reported outcome, HAM-A, assessed by a blinded clinician, is implemented to support the primary endpoint.

The proportion of PF patients with mild to moderate anxiety (scoring 5-14 on a 0-21 scale) may be as high as 60% in patients with PF (Coelho et al., 2010; Glaspole et al., 2017; Holland et al., 2014; Lee et al., 2017). Although live sessions with a psychotherapist providing traditional CBT could be effective for PF patients, psychological therapy or other mental health interventions are not part of standard of care in patients with PF (Raghu et al., 2015).

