8.2.1. General Anxiety Disorder-7

Anxiety severity will be assessed by GAD-7 by the subject using an electronic diary on their own smartphone, tablet device or computer.

The GAD-7 questionnaire includes the following questions (paper version displayed):

GAD-7 Anxiety

Over the last two weeks , how often have you been bothered by the following problems?		Several days	More than half the days	Nearly every day
Feeling nervous, anxious, or on edge	0	1	2	3
Not being able to stop or control worrying	0	1	2	3
Worrying too much about different things	0	1	2	3
Trouble relaxing	Ö	1	2	3
Being so restless that it is hard to sit still	0	1	2	3
Becoming easily annoyed or irritable	0	ì	2	3
Feeling afraid, as if something awful might happen	Ö	1	2	3

	Column totals	+	+ + =
			Total score
	olems, how difficult have the along with other people?	y made it for you to	do your work, take care of
Not difficult at all	Somewhat difficult	Very difficult	Extremely difficult

Source: Primary Care Evaluation of Mental Disorders Patient Health Questionnaire (PRIME-MD-PHQ). The PHQ was developed by Drs. Robert L. Spitzer, Janet B.W. Williams, Kurt Kroenke, and colleagues. For research information, contact [name] at [contact]. PRIME-MD® is a trademark of Pfizer Inc. Copyright® 1999 Pfizer Inc. All rights reserved. Reproduced with permission

The response scores of the first 7 questions are added to create a composite score (range 0-21), with higher scores indicating a higher level of anxiety.

Composite scores of \leq 4, 5-9, 10-14, and \geq 15 represent minimal, mild, moderate, and severe anxiety, respectively.

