- 10. In the last two weeks how much of the time have you felt your lung disease is getting worse?
- 1. All of the time
- 2. Most of the time
- 3. A lot of the time
- 4. Some of the time
- 5. A little of the time
- Hardly any of the time
- 7. None of the time
- 11. In the last 2 weeks has your lung condition interfered with your job or other daily tasks?
- 1. All of the time
- 2. Most of the time
- 3. A lot of the time
- 4. Some of the time
- 5. A little of the time
- Hardly any of the time
- 7. None of the time
- 12. In the last 2 weeks have you expected your lung symptoms to get worse?
- 1. All of the time
- 2. Most of the time
- 3. A lot of the time
- 4. Some of the time
- 5. A little of the time
- 6. Hardly any of the time
- 7. None of the time

[figure not shown]
- 13. In the last 2 weeks, how much has your lung condition limited you carrying things, for example, groceries?
- 1. All of the time
- 2. Most of the time
- 3. A lot of the time
- 4. Some of the time
- 5. A little of the time
- 6. Hardly any of the time
- 7. None of the time
- 14. In the last 2 weeks, has your lung condition made you think more about the end of your life?
- 1. All of the time
- 2. Most of the time
- 3. A lot of the time
- 4. Some of the time
- 5. A little of the time
- 6. Hardly any of the time
- 7. None of the time
- 15. Are you financially worse off because of your lung condition?
- 1. A significant amount
- 2. A large amount
- 3. A considerable amount
- 4. A reasonable amount
- 5. A small amount
- 6. Hardly at all
- 7. Not at all

Thank you for completing this questionnaire.

Scores will be calculated for each domain (breathlessness and activities, chest symptoms and psychological) and for the total questionnaire. The K-BILD domain and total scores ranges are 0-100; 100 represents the best health status.

PAIN / DISCOMFORT I have no pain or discomfort I have slight pain or discomfort I have moderate pain or discomfort I have severe pain or discomfort I have extreme pain or discomfort ANXIETY / DEPRESSION I am not anxious or depressed I am slightly anxious or depressed I am moderately anxious or depressed I am severely anxious or depressed

I am extremely anxious or depressed

[figure not shown]

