9.1. Statistical Hypotheses

The aim of this clinical investigation is to show superiority of dCBT-PF over a control group regarding selected efficacy measures. The null hypothesis to be tested for each endpoint will be that there is no difference between dCBT-PF and control, against the alternative hypothesis that dCBT-PF is better than control. All tests will be done using 2-sided alternatives.

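### Section 9.3.3 compares non-binary categorical endpoints with an unqualified chi2-test; any ordered endpoint among them should have an ordered analysis with an effect estimate

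*Combined protocol and SAP*

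**What the plan says.** Section 9.3.3 assigns a method to each type of endpoint. GAD-7, HAM-A, K-BILD and other continuous scores go to ANCOVA, and PGIC scores to ANOVA. Binary outcomes go to logistic regression with treatment and baseline anxiety stratum. For the rest it says: "Categorical endpoints will be summarized by category and compared using the chi2-test". The type of chi2-test is not named, no effect measure is given, and ordered categories are not treated separately.

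Section 9.1 sets the hypothesis for every endpoint as no difference, "against the alternative hypothesis that dCBT-PF is better than control". Section 9.3.1 adds "All tests will be 2-sided at a 5% significance level" and says that the actual stratification enters the analyses as factors.

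Several ordered responses are visible in section 8.2:

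- Five-level health items printed after the K-BILD text, for example "I am not anxious or depressed I am slightly anxious or depressed I am moderately anxious or depressed I am severely anxious or depressed", followed by an extreme level. Their own section heading and scoring text are not visible.
- The four GAD-7 classes in section 8.2.1, which "represent minimal, mild, moderate, and severe anxiety, respectively".
- The four-level GAD-7 difficulty question, which is outside the composite score.

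No visible text says how, or whether, these three are compared between arms. Section 9 also defers technical detail to a separate SAP.

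**The concern.** The usual chi2-test on a 2 × k table treats the k levels as unordered labels. Permuting the columns leaves the p-value unchanged. With five levels it spreads its power over 4 degrees of freedom, most of them describing patterns that nobody expects from the treatment. It can be significant when one arm has more answers at both ends of the scale and no net benefit.

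Two things would be at stake for an ordered endpoint. First, a real, moderate shift towards better categories would be missed more often than necessary. Second, the result would be a p-value alone. The other between-group comparisons in 9.3.3 come from models that estimate a treatment effect; this one does not. That second defect needs no power assumption.

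**Working it through.** The visible text gives no power, effect size or level distribution for any categorical endpoint, so there is no figure of the plan to reproduce. The check asks how much power is lost if such an endpoint is ordered.

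**Inputs from the document**

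- Two-sided 5% (9.3.1).
- Size (1.1): "Recruitment for Part 2 will continue until end July 2023, or when a maximum of 250 subjects with PF have been enrolled, whatever comes first". Allocation (4.2): "Subjects will be randomised 1:1 to dCBT-PF or an open-label waitlist control group". The maximum is therefore 250 / 2 = 125 per arm. Because recruitment can stop by date and subjects can drop out, 75 per arm is also shown.
- Five levels, as in the health items in 8.2.

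**Assumptions, not in the document**

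- Control distribution from best to worst level: 15%, 35%, 30%, 15%, 5%.
- A proportional-odds shift: if C is the cumulative control probability at a cut, the treated value is OR × C/(1−C) divided by 1 + OR × C/(1−C). For OR 2.0 at the first cut: 2 × 0.15/0.85 = 0.353, and 0.353/1.353 = 0.261. The full treated distribution is 26.1%, 40.6%, 22.2%, 8.5%, 2.6%.
- "chi2-test" is read as Pearson's test.

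**Check 1: degrees of freedom only.** Take the noncentrality λ that gives a 1-df test a set power, then read the power of a 4-df test at the same λ: P(χ²₄(λ) > 9.49).

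| 1-df power | λ | 4-df power | Loss (points) |
|---|---|---|---|
| 30% | 2.06 | 18% | 12 |
| 50% | 3.84 | 31% | 19 |
| 70% | 6.17 | 48% | 22 |
| 80% | 7.85 | 60% | 21 |
| 90% | 10.51 | 74% | 16 |
| 95% | 12.99 | 84% | 11 |

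**Check 2: simulation.** 20,000 trials per row, Pearson (4 df) against the tie-corrected Wilcoxon test. The simulation standard error is at most about 0.35 points (√(0.25/20,000)).

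| Per arm | OR | Pearson | Wilcoxon | Loss (points) |
|---|---|---|---|---|
| 125 | 1.3 | 12.5% | 21.0% | 8.5 |
| 125 | 1.5 | 25.2% | 42.6% | 17.4 |
| 125 | 1.75 | 46.0% | 68.0% | 22.0 |
| 125 | 2.0 | 66.3% | 85.4% | 19.1 |
| 125 | 2.5 | 90.3% | 97.8% | 7.5 |
| 125 | 3.0 | 97.9% | 99.8% | 1.9 |
| 75 | 1.3 | 8.6% | 14.3% | 5.7 |
| 75 | 1.5 | 15.5% | 27.3% | 11.8 |
| 75 | 1.75 | 27.2% | 46.6% | 19.5 |
| 75 | 2.0 | 41.7% | 64.4% | 22.6 |
| 75 | 2.5 | 67.0% | 86.6% | 19.6 |
| 75 | 3.0 | 84.0% | 95.6% | 11.6 |

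Four other assumed control shapes (uniform, middle-peaked, skewed, mild-to-moderate) gave similar losses. Over OR 1.5 to 2.0 and 75 to 125 per arm the loss ran from about 12 to 23 points, with a maximum of 23.3. At OR 1 both tests rejected in about 5% of trials.

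**Check 3: shifts that are not consistent.** With the same control distribution, 125 per arm, and a treated distribution of 20%, 25%, 25%, 20%, 10% (more answers at both ends), Pearson rejects in 50.8% of trials and Wilcoxon in 14.1%. In four non-proportional examples run separately at 125 per arm, Pearson was 12 to 73 points more powerful. The advantage of the ordered test therefore depends on the shift running the same way across levels.

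**The case against.** The strongest reply is that the document does not show that this trial has the problem. A reader might infer that the five-level items in 8.2 are compared by chi2, so that the trial does lose this power. The text does not support that. The exploratory endpoint list is not visible, nor is the text around the five-level items, so they may be scored, dichotomised or only tabulated. The visible uses of the GAD-7 classes are stratification and subgroups. The difficulty question is not named as an endpoint. HAM-A and K-BILD items feed scores analysed by ANCOVA, and PGIC is analysed as a score. The remaining categorical endpoints could be nominal. This stands, and is why the point is conditional.

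It is also fair that Pearson is an inference, although it is the natural reading of an unqualified chi2-test. Direction can be read informally from the by-category table that the same sentence requires, but the test still supplies no estimate or interval.

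The power figures are not the plan's. They rest on proportional odds, which favours the ordered test, and check 3 shows the reverse case.

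The deferral to the SAP does not remove the point. Section 9 says that the SAP will describe the analyses of that section in more detail; it does not say that the chi2 rule will be replaced.

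**Conclusion.** The point holds as a conditional, minor improvement. Section 9.3.3 states one rule for all non-binary categorical endpoints, and that rule does not suit an ordered one: it ignores the order and yields no direction or effect estimate.

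If an endpoint has five ordered levels and the effect is a proportional-odds shift, the cost is about 12 to 23 points of power at odds ratios of 1.5 to 2.0 with 75 to 125 analysed per arm. At 125 per arm it is about 8 points at odds ratios of 1.3 and 2.5, and about 2 at 3.0. For inconsistent shifts the chi2-test can be the more powerful one.

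It would be wrong to infer any effect on the trial's main conclusions. The primary and key secondary endpoints use ANCOVA. All other efficacy endpoints are exploratory, outside the testing hierarchy and without multiplicity adjustment.

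**What to change.** In 9.3.3 and the SAP, replace the chi2 sentence with:

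> Ordered categorical endpoints will be summarised by category and compared with a proportional-odds model with treatment and baseline GAD-7 stratum as factors, reporting the common odds ratio with 95% CI; a stratified rank test (van Elteren) is reported as a pre-specified sensitivity analysis. The chi2-test is used only for endpoints whose categories have no order.

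The stratum is included because 9.3.1 requires the stratification as a factor. The rank test is always reported, so no unspecified check of proportional odds decides which result counts. The SAP should also say which endpoints are ordered.

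The cost is a short text change and standard software, with no new data or subjects. If no endpoint is ordered, nothing changes. The one downside is lower power for differences that are not consistent across levels; these remain visible in the by-category table.
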